2.5 Objectives and end points summary

Primary Outcome Measures	
Maximum tolerable dose calculated after the completion of the dose-escalation	
completion of the dose-escalation	

2.6 Trial design

To improve transparency, completeness, reproducibility and trial usefulness of this early phase dose-finding trial, the Standard Protocol Items: Recommendations for Interventional Trials Dose-finding Extensions (SPIRIT-DEFINE) guideline ²⁵ has been followed. This is a dose-escalation, randomised controlled trial, where critically ill patients will receive either Omegaven or standard care for 10 days or until hospital discharge, whichever is sooner. The Bayesian Optimal Interval (BOIN) design is being used to specify the dose-escalation/ de-escalation decision strategy whereby the observed dose-limiting toxicity (DLT) at each dose level is

compared with a pair of escalation and de-escalation boundaries optimised to minimise the risk of patients receiving overly toxic or subtherapeutic doses.²⁶ The BOIN design implemented in HIPPO is similar to the traditional 3+3 design but provides more flexibility and possesses superior operating characteristics that are comparable to those of more complex model-based designs.²⁷

Dose-limiting toxicity assessment

DLT events and assessments will be treated separately from the overall pharmacovigilance described in section 13.0.

Patients will be screened for DLT events once a day (this can be at any point during a 24-hour period) from the start of the intervention until five hours after the completion of the last dose or hospital discharge, whichever occurs first. DLT event screening will also occur in control patients from days 1-11 to compare the event rates with the intervention arm. Screening for DLT events will occur by reviewing routinely collected clinical laboratory tests and clinical examination in the first place. Blood tests include electrolytes, glucose, serum creatinine, liver enzymes (serum ALT, AST, ALP, y-glutamyl transpeptidase) and total serum bilirubin, serum triglycerides, blood count (leukocytes, platelets, red blood cells, neutrophils, lymphocytes, monocytes, eosinophils, basophils, and nucleated red blood cell count) and coagulation measures (prothrombin time, PTR/INR, activated partial thromboplastin time), and acid-base metabolism. If these measures are not available routinely, they will be mandated by the research team. Similarly, daily vital sign measurements (heart rate, blood pressure, body temperature, fluid balance and respiratory rate) will be taken by the research team, if not performed as part of routine care. These results will be noted in the Case Report Form (CRF).

The DLT assessment will be performed by a three-member panel comprising of two independent assessors (Consultant Gastroenterologists) and the Chief Investigator (CI) after the completion of each dosing phase. The panel will be blinded to study arm allocation (intervention or control). In the event that the CI does become unblinded, the delegated sub investigator will replace the CI on the adjudication panel.

Potential DLT events are defined as either a pre-specified AE or serious adverse event (SAE) attributable to Omegaven, as listed in **Table 1.**^{28 29} The pre-defined AEs and SAEs have been taken from the "undesirable effects" section in the SmPC for Omegaven, considering effects deemed unacceptable. Thrombophlebitis has also been added to this list and the range for hyper-triglyceridaemia adjusted based on previously published data.³⁰ To make provision to address any undesirable effects not listed in the SmPC, "Other" has been added to Table 1 as well. These are medical events of concern to the consultant in charge of direct patient care

with potential to be related to Omegaven. Patients will be monitored by senior clinicians at least twice a day as part of standard care. On occurrence of a medical event of concern, the research team will be notified and will assess the event against the US National Cancer Institute guidance document of Common Terminology Criteria for Adverse Events (CTCAE) version 5.0 ³¹, and will record a potential DLT event, if the event is determined as Grade 3 or higher (Figure 1). Following the identification of an event listed in **Table 1**, relatedness to Omegaven will be assessed to determine if the event will be classified as a DLT event.³² This will be based on a tiered assessment (WHO-UMC causality categories, **Table 2**).³³ If the predefined AEs and SAEs in **Table 1** are deemed as definitely or probably/likely related to the intervention, they will be counted towards the DLT assessment.

[figure not shown]

Figure 1 Flow diagram for "Other" DLT identification: The figure describes the steps of identification of an "Other" DLT for the HIPPO trial.

CTCAE: Common Terminology Criteria for Adverse Events

Table 1: DLTs defined for the HIPPO trial

DLT events	Description	Initial identification	Criteria	Time scale for consideration	Action (related to trial)
Haemolysis	Widespread erythrocyte cell membrane destruction	Haemoglobin measured daily. Treating clinician requests haemolysis screen if indicated. -	- Laboratory evidence of haemolysis (e.g., direct antiglobulin test; schistocytes; decreased haptoglobin) AND - Loss of > 2 g haemoglobin within 24 hours (2 blood tests closest to 24 h apart) AND - Transfusion or medical intervention (i.e. steroids) indicated AND - No other potential cause than the intervention	Evidence of haemolysis within 24 hours of Omegaven infusion Transfusions that occur within 24 hours of diagnosis of haemolysis	- Document and contact CI
Hyper-triglyceridaemia	Elevated levels of triglycerides in blood	- Measured daily	- Triglycerides > 530.97 mg/dl (6 mmol/l) ³⁰	If occurs at any point during the infusion or within five half-lives (5 hours) of finishing the infusion	Stop infusion Document and contact CI
Reticulocytosis	Increase in circulating reticulocytes (immature red blood cells) as sign of accelerated erythrocyte production	- Measured daily.	Reticulocytes >100 x10 ⁹ /I ³⁴ AND No other potential cause than the intervention AND Need for transfusion within 24 hours of diagnosis	- Need for transfusion within 24 hours of diagnosis	- Document and contact CI
Thrombocytopenia	Deficiency of blood platelets	- Measured daily.	 Platelets <50 x10⁹ with requirement of platelet transfusion AND 	Within 24 hours of infusionTransfusions that occur within 24 hours	- Document and contact CI

HIPPO V3.0 14/02/2025 Page 19 of 62

			Absence of other causes of thrombocytopenia such as therapeutic agents (e.g. heparin), chronic diseases	of diagnosis of thrombocytopenia	
Thrombophlebitis	Inflammation in the vein in the presence of an intravenous catheter	 Identified on clinical examination by staff or by patient if conscious. Absence of documentation will be considered to indicate no concern. 	 Grade 3 (Pain at the puncture site with erythema, hardening and a palpable venous cord) OR Grade 4 (Pain at the puncture site with erythema, hardening and a palpable venous cord that is > 1 cm, with purulent discharge) 	If occurs within 24 hours of any Omegaven infusion, specific to the cannula used to infuse Omegaven.	- Document and contact CI
Urticaria	A skin reaction/rash with itchy welts	 Identified on clinical examination by staff or by patient if conscious. Absence of documentation will be considered to indicate no concern. 	- > 30% body surface areaAND- Requiring IV intervention	- Diagnosis within one hour of Omegaven infusion	- Document and contact CI
Other	Medical event of concern to the consultant with clinical responsibility to patient possibly related to Omegaven	Concern to the consultant in charge and notification of research team	- ≥ Grade 3 event in CTCAE ³¹	If occurs at any point during the infusion or within five half-lives (5 hours) of finishing the infusion	- Document and contact CI

CTCAE: Common Terminology Criteria for Adverse Events v 5.0

HIPPO V3.0 14/02/2025 Page 20 of 62

Table 2: WHO-UMC Causality Categories³³

Causality term	Assessment Criteria*
Certain	Event or laboratory test abnormality, with plausible time relationship
	to drug intake
	Cannot be explained by disease or other drugs
	Response to withdrawal plausible (pharmacologically, pathologically)
	Event definitive pharmacologically or phenomenologically (i.e. an objective
	and specific medical disorder or a recognised pharmacological
	phenomenon)
	Rechallenge satisfactory, if necessary
Probable/	• Event or laboratory test abnormality, with reasonable time relationship to drug
Likely	intake
	Unlikely to be attributed to disease or other drugs
	Response to withdrawal clinically reasonable
	Rechallenge not require
Possible	• Event or laboratory test abnormality, with reasonable time relationship to
	drug intake
	Could also be explained by disease or other drugs
	Information on drug withdrawal may be lacking or unclear
Unlikely	• Event or laboratory test abnormality, with a time to drug intake that makes a
	relationship improbable (but not impossible)
	Disease or other drugs provide plausible explanations
Conditional/	Event or laboratory test abnormality
Unclassified	More data for proper assessment needed, or
	Additional data under examination
Unassessable/	Report suggesting an adverse reaction
Unclassifiable	Cannot be judged because information is insufficient or contradictory
	Data cannot be supplemented or verified

^{*}Validity of criteria should be judged by independent adjudicator panel

Dose-escalation plan

The BOIN intervention algorithm for the HIPPO trial is shown in **Figure 2**. ³⁵ ³⁶ Cut-offs for the escalation and de-escalation boundaries for the DLT rate were obtained using software available at www.trialdesign.org, using the following input parameters:

- three doses
- target toxicity rate for the maximum tolerable dose 0.30 (30%)
- patients recruited in cohorts of nine,
- maximum sample size is 27
- 0.80 probability cut-off for overdose control

Upon the completion of each dosing phase (defined as at least five hours after the last patient in the phase has finished the last dose of Omegaven), the DLT rate will be computed as follows, and compared with the cut-offs shown in **Figure 2** before treating the next cohort of patients:

DLT rate = Number of patients who experienced DLT at current dose

Total number of evaluable patients treated on current dose

Following the DLT assessment and based on the DLT rate, the next nine intervention patients will either:

- 1) receive the next highest dose if the observed DLT rate on the current dose is ≤0.236
- 2) remain on the same dose if the observed DLT rate is >0.236 and <0.359
- 3) de-escalate to the next lowest dose if the observed DLT rate is >0.359

If de-escalation is indicated on the lowest dose, the next cohort of patients will continue at the lowest dose. If the probability of the observed DLT rate being greater than the target DLT is >0.80 and if at least three patients are treated at the current dose, the dose is too toxic. Therefore, this dose and any higher doses will be eliminated. If the lowest dose is too toxic, the trial must be terminated.

After the panel meeting that will be held following completion of each dosing phase, a report will be drafted and agreed on by all panel members in a timely manner. The report which will include the recommended dosing plan for the next cohort of patients will be signed off by the trial statistician within two weeks of receipt. Once these approvals are in place, the next cohort of patients will be recruited. These approvals will be filed in the ISF and TMF. Each DLT assessment report will also be reported to the Data Monitoring and Ethics Committee (DMEC) for information only.

[figure not shown]

Figure 2 Intervention algorithm: The figure describes the BOIN dose-escalation and de-escalation plan for the HIPPO trial. At each stage, the DLT events rate will be used to assess whether the dose will be escalated, retained, or de-escalated. The stopping rule at each dosing phase is defined as "Is the maximum sample size reached?". After the stopping rule is met, the maximum tolerable dose (MTD) will be calculated, which is the primary outcome of the trial. Note: If the lowest dose is eliminated due to

DLT = Dose-limiting toxicity, from a list of pre-specified adverse or serious adverse events attributable to Omegaven (Table 1).

toxicity the trial is stopped, and no maximum tolerable dose can be obtained.

BOIN design implementation

The following steps detail the BOIN design implementation plan for the HIPPO trial.

- 1. Treat patients in the first cohort (nine patients) at the lowest dose (0.2 g/kg/d) of Omegaven
- 2. Perform DLT assessment as described above
- 3. Calculate DLT rate

DLT rate = Number of patients who experienced DLT at current dose

Total number of evaluable patients treated on current dose

- 4. Assign a dose to the next cohort of patients:
 - Conduct dose-escalation/de-escalation according to the rule displayed in **Table 3**. Notes for using Table 3:
 - a. "Eliminate" means eliminate the current and higher doses from the trial to prevent treating any future patients at these doses because they are overly toxic.
 - b. When a dose is eliminated, the next cohort is automatically de-escalated to the dose on the next lower level. When the lowest dose is eliminated, the trial is stopped for safety. In this case, no dose should be selected as the maximum tolerable dose.
 - c. If none of the actions (i.e., escalation, de-escalation or elimination) is triggered, the new cohort of patients are treated at the current dose.
 - d. If the current dose is the lowest dose and the rule indicates dose de-escalation, the new cohort of patients should be treated at the lowest dose unless the number of DLT events reaches the elimination boundary, at which point the trial is stopped for safety.
 - e. Number of DLT events in **Table 3** is the number of patients with at least one DLT events, therefore a patient will only be counted once for DLT events assessment, independent of the number of DLT events the patient experiences.
- Repeat step four until the maximum sample size of 27 patients receiving the intervention is reached, or stop the trial early if the number of patients experiencing DLT events at the lowest dose level reaches the elimination boundaries listed in **Table** In the latter case, no dose should be selected as the maximum tolerable dose.

Table 3 Escalation/De-escalation Rule for the HIPPO trial: The table details the rules when to escalate, retain, de-escalate or eliminate a treatment dose in the HIPPO trial, based on number of patients with DLT events (Table 1), considering the total number of patients treated with that dose. For HIPPO, cohorts of nine (highlighted columns) are treated. The last row represents the number of patients with DLT events at which the dose is deemed too toxic, and that dose and any higher dose will be eliminated.

Escalation/De-escalation Rule

Number of evaluable patients treated	3	4	5	6	7	8	9	10	11	12	13	14	15	16	17	18	19	20	21	22	23	24	25	26	27
Escalate if # of DLT <=	0	0	1	1	1	1	2	2	2	2	3	3	3	3	4	4	4	4	4	5	5	5	5	6	6
Stay if # of DLT =	1	1	NA	2	2	2	3	3	3	3-4	4	4-5	4-5	4-5	5-6	5-6	5-6	5-7	5-7	6-7	6-8	6-8	6-8	7-9	7-9
De-escalate if # of DLT >=	2	2	2	3	3	3	4	4	4	5	5	6	6	6	7	7	7	8	8	8	9	9	9	10	10
Eliminate if # of DLT >=	2	2	3	3	3	4	4	5	5	5	6	6	6	7	7	7	8	8	8	9	9	9	10	10	10

DLT = dose-limiting toxicity

of DLT is the number of patients with at least 1 DLT

NA = not applicable (no rule available for staying on same dose in this scenario – plan is to either escalate or deescalate)

Further notes:

Dose-escalation will occur if applicable, to the second (0.4 g/kg/d Omegaven) and third dose (0.6 g/kg/d Omegaven). If no dose-escalation can be performed, another nine participants will either be treated at the same or the lower dose, guided by the dose-escalation plan, leading to 27 patients receiving the intervention, and an additional 9 patients in the control group, to reach the maximum sample size of 36 patients.

The trial will stop if the stopping rule is met (once the maximum sample size for the trial has been reached), irrespective of which doses have been tested; or if the elimination rule is met on the lowest dose (the lowest dose is found to be too toxic) (lowest row in **Table 3**). The maximum sample size for this trial is 36 patients (27 patients receiving the intervention in cohorts of 9 patients, plus 9 control patients).

For example, after treating nine patients in one phase of the dose-escalation trial the DLT events rates in **Figure 2** translate to the following, as described in **Table 3**:

- If ≤2 patients experience DLT events, the dose can increase to the next higher dose
- If 3 patients experience DLT events, another nine patients will be treated with the same dose
- If ≥4 patients experience DLT events, the current dose and higher doses are eliminated, and the dose has to be de-escalated to the next lower dose.

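### The haemolysis DLT reads the haemoglobin fall from two tests picked only by their 24-hour spacing, so a red-cell transfusion between them can hide the fall and leave some treated haemolysis uncounted

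*Protocol*

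**What the plan says.** The haemolysis row of Table 1 (protocol section 2.6) lists four criteria, each joined to the next by AND:

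1. "Laboratory evidence of haemolysis (e.g., direct antiglobulin test; schistocytes; decreased haptoglobin" (parenthesis closed in the source);
2. "Loss of > 2 g haemoglobin within 24 hours (2 blood tests closest to 24 h apart" (likewise);
3. "Transfusion or medical intervention (i.e. steroids) indicated";
4. "No other potential cause than the intervention".

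The identification column gives the testing frequency as "Haemoglobin measured daily" and leaves the haemolysis screen to the treating clinician. The time-scale column adds "Transfusions that occur within 24 hours of diagnosis of haemolysis".

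The row does not say whether the second haemoglobin must precede a transfusion, and it makes no allowance for transfused blood. The 2 g threshold has no denominator.

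The number of patients with at least one DLT is then compared with Table 3. At nine evaluable patients the rule is to escalate at 2 or fewer, stay at 3, and de-escalate and eliminate at 4 or more.

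**The concern.** Criteria 2 and 3 work against each other. Criterion 3 asks whether the patient needed treatment, and transfusion is one such treatment. Transfusion raises haemoglobin, which is what criterion 2 measures. If red cells are given between the two tests, the later value reflects both the haemolysis and the transfusion, and the difference understates the fall. Because all four criteria must hold, the event is then not identified under this row. Section 2.6 assesses relatedness only after a Table 1 event has been identified, so a masked case need not reach the causality step.

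The DLT count drives every dose decision and feeds the isotonic estimate of the maximum tolerable dose in section 15.4. Masking can only lower that count. It also makes the count depend on when the treating team transfuses, in a trial where section 8.5 says treatment is open label.

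**Working it through.** **Step 1. Reproduce the decision rule.** The inputs in section 2.6 are a target rate φ = 0.30, cohorts of nine and an overdose cut-off of 0.80. The protocol does not state the two alternative rates, so the usual BOIN defaults are assumed: p1 = 0.6 × 0.30 = 0.18 and p2 = 1.4 × 0.30 = 0.42.

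- Escalation boundary: ln[(1 − p1)/(1 − φ)] / ln[φ(1 − p1)/(p1(1 − φ))] = ln(0.82/0.70) / ln(0.246/0.126) = 0.2365. The protocol gives 0.236.
- De-escalation boundary: ln[(1 − φ)/(1 − p2)] / ln[p2(1 − φ)/(φ(1 − p2))] = ln(0.70/0.58) / ln(0.294/0.174) = 0.3585. The protocol gives 0.359.
- At n = 9: 9 × 0.2365 = 2.13, so escalate at 2 or fewer; 9 × 0.3585 = 3.23, so de-escalate at 4 or more.
- Elimination, with a Beta(1,1) prior: P(rate > 0.30) is 0.650 at 3/9 and 0.850 at 4/9, so eliminate at 4 or more.

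All of this agrees with Table 3. The decision rule is sound; the question is what is counted into it.

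**Step 2. Effect of a transfusion between the two tests.** Let D be the fall that would have been seen without transfusion, u the number of red-cell units given between the tests, and r the rise per unit. The protocol does not give r; 0.5 to 1.5 g/dl is assumed. The threshold is read as g/dl, also an assumption because the unit is missing.

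Observed fall = D − u × r, so the criterion is met only if D > 2 + u × r.

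| Units between tests | r = 0.5 | r = 1.0 | r = 1.5 |
|---|---|---|---|
| 1 | D > 2.5 | D > 3.0 | D > 3.5 |
| 2 | D > 3.0 | D > 4.0 | D > 5.0 |

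Falls above 2 g/dl that do not exceed these values are missed.

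**Step 3. Example.** Haemoglobin is 10.0 g/dl at 06:00 and 7.5 at 18:00. One unit is given, and the next test is at 06:00. Before the transfusion the fall is 10.0 − 7.5 = 2.5, which exceeds 2. If nothing else changes, the next morning's value is 7.5 + 0.5 to 7.5 + 1.5, that is 8.0 to 9.0. The 24-hour pair then shows a fall of 1.0 to 2.0, which does not exceed 2.

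**Step 4. Effect on the dose decision.** At n = 9, one uncounted patient with no other DLT moves 3 to 2 (stay becomes escalate) or 4 to 3 (eliminate becomes stay).

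For scale only, suppose the true DLT rate is 0.40 and a share m of all DLT patients goes uncounted. The count is then binomial with n = 9 and rate 0.40 × (1 − m):

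| m (assumed) | Effective rate | P(escalate) | P(eliminate) |
|---|---|---|---|
| 0% | 0.40 | 0.232 | 0.517 |
| 10% | 0.36 | 0.314 | 0.416 |
| 20% | 0.32 | 0.411 | 0.317 |
| 30% | 0.28 | 0.517 | 0.226 |

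Here m is a share of all DLT patients, and haemolysis is only one of six named toxicities. The table shows how sensitive the rule is; it does not estimate the loss.

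**The case against.** Five points can fairly be made on the other side.

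- **Not every treated case is masked.** A reader might infer that any treated haemolysis escapes the count. The protocol does not support that. Steroids also satisfy the treatment criterion and do not mask the fall in this way, and a transfusion after the second test hides nothing. This limits the point to transfusions between the two tests.
- **The worst cases need not drop out.** A reader might also infer that the most severe haemolysis is lost. By step 2, a large fall still exceeds 2 g net of the transfusion. Severe cases are lost only if the transfused volume keeps pace, and nothing in the protocol shows that. The loss falls on moderate, promptly transfused cases.
- **Another pair may be available.** If a test was taken about 24 hours before the pre-transfusion value, that pair also fits the wording and shows the fall. This stands as a limit on frequency. It also confirms that the row does not settle which pair applies.
- **Other rows may catch the patient.** The reticulocytosis row has no haemoglobin-fall criterion and includes need for transfusion, so it may pick up some cases, though it has its own count threshold. The Other row is a weaker backstop: section 2.6 introduces it for "any undesirable effects not listed in the SmPC", it depends on consultant concern, and its window ends five hours after the infusion.
- **The column mismatch may be only loose wording.** The time-scale column can be read as bounding when transfusions count, leaving steroid cases to the criteria column. That reading is reasonable, so this is a gap to close and not a proven conflict.

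**Conclusion.** The concern holds in a limited form. As written, the row can fail to count a haemolysis event that was both present and treated, because one required condition can mask another. The affected cases are moderate falls with red cells given between the two tests: above 2 g/dl but not above about 2.5 to 3.5 g/dl after one unit, if the assumed rise of 0.5 to 1.5 g/dl per unit is right. The direction is towards fewer DLTs and towards escalation, and at nine patients a single pivotal case changes the decision.

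A reader might conclude that the maximum tolerable dose will be overstated by some known amount. The protocol does not support that. It gives no haemolysis rate and no transfusion timing, so the frequency cannot be computed and may be small. The patient must also be pivotal, have no other DLT, and meet the laboratory and no-other-cause criteria.

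The missing unit (per dl and per l differ tenfold) and the mismatch between columns are wording points. They would not carry the finding alone, but they belong in the same edit. The row should be corrected; the BOIN rule itself is unaffected.

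**What to change.** Amend the haemolysis row of Table 1 and its adjudication form:

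- Keep the 24-hour pair when no red cells were given between the two tests.
- When red cells were given between them, take the last haemoglobin before the transfusion (normally the lowest) as the second value, and compare it with the earlier value within the preceding 24 hours. In the step 3 example this gives 10.0 − 7.5 = 2.5, so the criterion is met; the other three criteria still apply.
- Say how the panel handles a case with no haemoglobin between the earlier test and the transfusion, since the fall cannot then be measured.
- State the unit of the 2 g threshold.
- Reconcile the criteria column with the time-scale column, so that both say whether treatment must be indicated or given and whether steroids count.

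A general highest-minus-lowest rule over 24 hours is not needed. It would also pick up short-term fluctuation in patients who were never transfused.

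The cost is a wording change. Section 8.2 already lists laboratory values and blood transfusions among the routinely collected data, so no new data are required. Slightly more events may go to the panel.

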For safety reporting all patients receiving the IMP will be assessed at least until five hours after the last infusion has stopped. This is based on 1) the triglyceride half-life for Omegaven being 54 minutes according to the SmPC and 2) the Council for International Organisations of Medical Sciences recommendation to collect Adverse Events (AEs) for at least an additional five half-lives of the IMP, after IMP administration.²⁴

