7.0 Trial intervention

Following consent, the intervention will start within 48 hours of critical care admission and continue for 10 days or until hospital discharge, whichever is sooner. Participants will receive either standard care or Omegaven.

Standard care arm

Patients in the standard care group will be managed by clinical staff according to local policy and guidelines until hospital discharge. Standard care includes receiving enteral nutrition according to the dietitian's advice.

Intervention arm

Participants will be randomised sequentially in three dosing phases (0.2, 0.4, 0.6 g/kg/d Omegaven) according to the BOIN dose-escalation plan (**Figure 2**, and section below).^{35 41} Omegaven will be provided based on bodyweight in kg, except in cases of morbidly obese patients (actual bodyweight > 200% of the ideal bodyweight). In this case, adjusted body weight will be used for Omegaven dosing, using the following formula:

Adjusted bodyweight = ideal body weight + (0.4 x (actual body weight – ideal bodyweight)).11

Patients will receive intravenous Omegaven to be administered daily (at any time within a 24-hour period) until day 10 or hospital discharge, whichever is sooner. Omegaven will be administered via a central line if available and if this is not possible it will be given peripherally. The timing of Omegaven administration will be determined in conjunction with the direct care team to ensure intervention delivery can be integrated with direct clinical care. Omegaven will be administered by an appropriately trained and qualified member of the research team, named on the delegation log. Treatment breaks are permitted for clinical reasons, with delivery of <80% of the intervention being considered a deviation.

The infusion rate of Omegaven will be initially set at 0.5 ml Omegaven/kg body weight/hour as specified in the SmPC (maximum infusion rate). For example, a 100 kg patient receiving 0.6 g/kg/d Omegaven would require a 12-hour infusion. The rate can be reduced if there is a clinical indication (e.g. small-bore peripheral canula, or uncontrolled diabetes mellitus (defined as diabetic ketoacidosis, or hypoglycaemic hyperosmolar state, as decided by the critical care consultant with responsibility for patient care)). Further guidance will be provided in the trial specific SOP.

8. Study Schedule

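### The daily triglyceride sample is not tied to the infusion, so hyper-triglyceridaemia DLTs can go unrecorded, and the share missed is largest at 0.2 g/kg/d

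*Protocol*

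**What the plan says.** The hyper-triglyceridaemia row of Table 1 (Protocol, section 2.6) sets the threshold at 6 mmol/l, lists the test as daily, and restricts the event in time: "If occurs at any point during the infusion or within five half-lives (5 hours) of finishing the infusion". The action is to stop the infusion.

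On where the value comes from, section 2.6 says "Screening for DLT events will occur by reviewing routinely collected clinical laboratory tests and clinical examination in the first place", and for gaps, "If these measures are not available routinely, they will be mandated by the research team". Neither sentence gives a time of draw. Section 2.6 also says "Patients will be screened for DLT events once a day (this can be at any point during a 24-hour period". That sentence governs when the screening review is done, not when blood is taken.

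Section 7.0 leaves the infusion equally free: "Patients will receive intravenous Omegaven to be administered daily (at any time within a 24-hour period", and "The timing of Omegaven administration will be determined in conjunction with the direct care team". The rate is common to all doses: "The infusion rate of Omegaven will be initially set at 0.5 ml Omegaven/kg body weight/hour as specified in the SmPC (maximum infusion rate". The schedule in section 8.1 shows only a daily DLT and safety review.

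**The concern.** The event is defined by time since the infusion, but nothing places the measurement at such a time. A sample drawn outside the window cannot yield a countable DLT, whatever the patient's peak was, and no later analysis can recover it.

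Because the infusion lengthens with dose, the chance of looking at the right time rises with dose. Part of any observed dose-toxicity gradient would then reflect detection. The first BOIN decision, on nine patients at 0.2 g/kg/d, is made where detection is poorest. A missed exceedance also never triggers the instruction to stop the infusion.

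**Working it through.** **Inputs from the protocol.** Rate 0.5 ml/kg/h (7.0); 10 g per 100 ml, i.e. 0.1 g/ml (11.1); doses 0.2, 0.4 and 0.6 g/kg/d; window of infusion plus 5 h (Table 1); "the triglyceride half-life for Omegaven being 54 minutes according to the SmPC" (1.3); escalate on at most 2 DLTs in 9 (Table 3).

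**Step 1: infusion time.** T = dose / (0.5 × 0.1 g/kg/h). At 0.6 this gives 0.6/0.05 = 12 h, which reproduces the worked example in section 7.0.

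**Step 2: counting window.** T + 5 h, as a share of 24 h.

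| Dose (g/kg/d) | T | Window | Share of day |
|---|---|---|---|
| 0.2 | 4 h | 9 h | 9/24 = 38% |
| 0.4 | 8 h | 13 h | 13/24 = 54% |
| 0.6 | 12 h | 17 h | 17/24 = 71% |

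Counted from the infusion start, a sample at 0–9 h can count at every dose, at 9–13 h only at 0.4 and 0.6, at 13–17 h only at 0.6, and at 17–24 h (7/24 = 29% of the day) at none. For example, if routine bloods are taken at 06:00 (assumed) and the infusion starts between 09:00 and 12:00, the sample falls 18–21 h after the start and misses the window every day at all three doses. At half the infusion rate the windows become 13, 21 and 24 h, so 0.2 still has the shortest.

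**Step 3: what a sample would read.** Assume linear one-compartment kinetics with half-life 0.9 h. The rise as a share of plateau at t hours is (1 − 2^(−min(t,T)/0.9)) × 2^(−max(t−T,0)/0.9).

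- Peak: 95%, 99.8% and 100% at 0.2, 0.4 and 0.6.
- At 6 h: 20%, 99% and 99%. At 8 h: 4%, 99.8% and 99.8%.

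On this model an exceedance is nearly as likely at 0.2 as at 0.6, but visible for a shorter time. If the threshold lies at 75% of the plateau rise, triglycerides exceed it for 2.5, 6.6 and 10.6 h.

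**Step 4: share of true exceedances recorded.** Simulation of 20,000 patients per setting with ten daily samples. None of these inputs is in the protocol: baseline 1.5–2.5 mmol/l, coefficient of variation (CV) of the rise 0.3–0.8, 10–42% of patients above 6 mmol/l at plateau, sample time uniform over the day relative to the infusion.

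| Sampling habit | 0.2 | 0.4 | 0.6 |
|---|---|---|---|
| Time redrawn each day | 47–71% | 85–95% | 98–99% |
| Habitual time, SD 2 h | 28–37% | 45–55% | 64–71% |
| Fixed time per patient | 7–13% | 19–29% | 36–47% |

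**Step 5: first decision at 0.2.** Exact binomial P(X ≤ 2 of 9), triglyceride DLTs only, all judged related, comparing full detection with 61% (within the first row of step 4).

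| True rate | Recorded rate | Escalate, full | Escalate, 61% |
|---|---|---|---|
| 10% | 6.1% | 95% | 99% |
| 20% | 12.2% | 74% | 91% |
| 30% | 18.3% | 46% | 78% |
| 40% | 24.4% | 23% | 62% |

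**Step 6: slower clearance.** With a 3 h half-life, CV 0.5 and 30% above threshold at plateau, the true rates are 6%, 19% and 26% and the recorded rates 3%, 14% and 22%. Much of the gradient is then real, and escalation from 0.2 is 98.6% with full detection against 99.8%.

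**The case against.** The strongest reply concerns size. Sections 1.1 and 1.3 present fish oil at 0.1–0.2 g/kg/d as allowed by guidelines and well tolerated, and section 6.2 excludes severe hyperlipidaemia. No document supports a 40% exceedance rate at 0.2, although patients with severe liver insufficiency are admitted, so high rates are not ruled out. Ten daily samples also help: if triglycerides stayed above threshold for the whole window on all ten days and sample times were independent, only 0.625^10 = 0.9% would be missed at 0.2. That is the best case; regular ward hours work against it. The size objection stands, and it limits how far the point can be pressed.

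Three stronger readings are tempting and should be resisted.

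- A reader might infer that most missed events occur at 0.2. That holds only as a share. In step 6 the missed percentage points are 3, 5 and 4, fewest at 0.2.
- A reader might infer that the trial is likely to escalate past a toxic dose. That needs common triglyceride DLTs. At true rates at or below the 30% target, extra escalation is not an overdose error. At the 54-minute half-life, a higher dose adds duration but almost no peak.
- A reader might infer that the whole DLT rate is affected. Hyper-triglyceridaemia is one of seven rows in Table 1, and each event must still be judged at least probably related.

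Section 7.0 refers to a trial-specific SOP that is not shown. The reference follows the infusion-rate text and does not mention triglyceride sampling. The time limit on the event is set in the protocol, so the matching draw time belongs there too.

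**Conclusion.** The point holds as a gap in data collection. From the protocol alone, a compliant site can sample when an exceedance cannot count, and the counting window covers 38%, 54% and 71% of the day at 0.2, 0.4 and 0.6 g/kg/d. The direction is a downward bias in the triglyceride component, with the largest share missed at 0.2.

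The size is conditional on exceedance rate, clearance and sampling habits, none of which the protocol gives. It is small near a true 10% and large only if triglyceride DLTs are common. Confidence is high on the gap and moderate on its practical weight. This is a worthwhile, cheap improvement; it does not show that the dose-finding design is unsound.

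**What to change.** In section 2.6 and the hyper-triglyceridaemia row of Table 1:

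- Require the planned daily triglyceride sample in the last hour of the infusion at every dose. Under the assumptions of step 4 this records 97–100% of true exceedances at the 54-minute half-life, and about 93–99% at 3 h with CV 0.5.
- Keep the rule that any earlier routine value above 6 mmol/l stops the infusion.
- Record the sample time and the infusion start and stop times in the eCRF. Tell the panel whether the sample fell inside the counting window, because the causality categories in Table 2 ask about time relationship.
- Give controls a nominal matching draw time, so that arm event rates are compared on the same footing.

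A sample about 4 h after the start should not replace the last-hour draw. With a 3 h half-life and CV 0.3 it records as little as 2–12% of exceedances at 0.4 and 0.6. It may be added as an early safety check.

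The BOIN rule, doses, infusion rate and MTD analysis are unchanged. The costs are less freedom in timing, an occasional extra draw (section 2.6 already lets the research team mandate missing tests) and three recorded times. A last-hour result comes too late to stop that day's dose, but the present text guarantees no earlier sample either.
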